7.2.5 Sponsor Responsibility for Reporting Adverse Events

All Adverse Events will be reported to regulatory authorities, IRB/IECs and investigators in accordance with all applicable global laws and regulations, i.e., per ICH Topic E6 (R1) Guidelines for Good Clinical Practice.

7.3 TRIAL GOVERNANCE AND OVERSIGHT

7.3.1 Scientific Advisory Committee

This trial was developed in collaboration with a Scientific Advisory Committee (SAC). The SAC comprises both Sponsor and non-Sponsor scientific experts who provide input with respect to trial design, interpretation of trial results and subsequent peer-reviewed scientific publications.

8.0 STATISTICAL ANALYSIS PLAN

This section outlines the statistical analysis strategy and procedures for the study. Changes to analyses made after the protocol has been finalized, but prior to final database lock, will be documented in a supplemental statistical analysis plan (sSAP) and referenced in the Clinical Study Report (CSR) for the study. Post hoc exploratory analyses will be clearly identified in the CSR.

8.1 Statistical Analysis Plan Summary

Key elements of the statistical analysis plan are summarized below; the comprehensive plan is provided in Sections 8.2 through 8.11.

Study Design Overview	A Phase II, open-label, multicenter, multi-arm trial to study the efficacy and safety of the combination regimen of MK-3682+MK-8408 in cirrhotic or non-cirrhotic subjects with chronic HCV GT1, GT2, GT3, GT4, GT5 or GT6 infection. Subjects will receive the combination regimen of MK-3682+MK-8408 for 12 weeks. Subjects may be HCV mono-infected or HIV-co-infected, treatment-naïve or treatment-experienced with a prior interferon-based therapy.
Treatment Assignment	Approximately 250 subjects will be enrolled into six cohorts receiving MK-3682 + MK-8408 for 12 weeks based on the genotype of their HCV infections. Although within six cohorts subjects will receive the same treatment regimen, i.e., MK-3682 + MK-8408 for 12 weeks, these cohorts are designated as six “treatment arms” in the study.
Analysis Populations	Efficacy: Per Protocol (PP), modified Full Analysis Set (mFAS) and Full Analysis Set (FAS) Safety: All Subjects as Treated (ASaT)
Primary Endpoint(s)	Proportion of subjects achieving SVR ₁₂ after 12 weeks of treatment
Key Secondary Endpoints	Proportion of subjects achieving SVR ₂₄ after 12 weeks of treatment, respectively. Proportion of subjects experiencing virologic failure at FW12 among all subjects who do not discontinue study for non-treatment-related reasons after 12 weeks of treatment, respectively.
Statistical Methods for Key Efficacy Analyses	For the primary efficacy analysis based on the PP population, the proportions of subjects achieving SVR ₁₂ will be estimated in each

	
treatment arm, and 95% confidence intervals (CIs) for these rates will be calculated using the Clopper-Pearson method [49]. The missing data approach of Treatment-Related Discontinuation=Failure (TRD=F) will be utilized for the primary analysis. The same Clopper-Pearson method will be used to analyze all binary endpoints based on the mFAS population for each treatment arm with TRD=F as the missing data approach and based on the FAS population for each treatment arm with Missing=Failure (M=F) as the missing data approach.

Statistical Methods for Key Safety Analyses	
The All-Subjects-as-Treated population will be employed for safety analyses. The proportion of subjects with adverse experiences of elevated laboratory values that are reported as ECIs described in section 7.2.3.2 during the study therapy period are prespecified as events of clinical interest and will be provided along with the corresponding 95% CIs.
 
In addition, the broad clinical and laboratory AE categories consisting of the percentage of subjects with any AE, a drug related AE, a SAE, an AE which is both drug-related and serious, and who discontinued due to an AE will be summarized in the same manner.

Interim Analyses	
Sentinel cohorts (i.e. first 10 subjects) in each treatment arm for GT1, GT2, GT3, and GT4 subjects will be assessed to determine the treatment duration for the main cohorts (i.e. the remaining subjects still on treatment).

Multiplicity	
No multiplicity adjustment is planned for the study.

Sample Size and Power	
Approximately 250 subjects will be allocated into one of the six treatment arms of combination of MK-3682 (450mg) and MK-8408 (60mg) for 12 weeks with 50 GT1-, 50 GT2-, 50 GT3-, 50 GT4-, 25 GT5- and 25 GT6-infected subjects in Arms 1, 2, 3, 4, 5 and 6, respectively Assuming a protocol violation rate of 10%, the PP population will include approximately 45 subjects in each of Arms 1, 2, 3 and 4. If the SVR₁₂ rate is approximately 96% (43 successes out of 45), the exact 95% CI is (84.9%, 99.5%). The PP population will include approximately 22 subjects in Arms 5 and 6. If the SVR₁₂ rate is approximately 91% (20 successes out of 22), the exact 95% CI is (70.8%, 98.9%). Detailed information is in Section 8.9.1.

8.2 Responsibility for Analyses/In-House Blinding

The statistical analysis of the data obtained from this study will be the responsibility of the Clinical Biostatistics department of the Sponsor.

This trial is being conducted as an open-label study, i.e., subjects, investigators, and Sponsor personnel will be aware of subject treatment assignments after each subject is enrolled and treatment is assigned. Through the course of this open-label study, efficacy and safety analyses may be performed by the Sponsor to monitor trends and facilitate programmatic decisions. In particular, when at least half of the subjects have reached FW4 and/or FW8, initial assessment of SVR₄ and/or SVR₈ may be performed.

8.3 Hypotheses/Estimation

Objectives of the study are stated in Section 3.0.

8.4 Analysis Endpoints

Efficacy and safety endpoints that will be evaluated are listed in the following sections.

8.4.1 Efficacy /Pharmacokinetics Endpoints

8.4.1.1 Efficacy Endpoints

An initial description of efficacy measures is provided in Section 4.2.3.1.

The primary efficacy endpoint is the proportion of subjects achieving SVR₁₂ after 12 weeks of treatment.

The secondary efficacy endpoints are:

- 1) the proportion of subjects achieving SVR₂₄ after 12 weeks of treatment.
- 2) the proportion of subjects experiencing virologic failure (either on-treatment failure or relapse post-treatment) at Follow-up Week 12 after 12 weeks of treatment, among all subjects who do not discontinue the study for non-treatment-related reasons.

8.4.1.2 Pharmacokinetics Endpoints

Additional details are in Section 4.2.3.3.

The primary PK endpoint for MK-3682 (and metabolites) and MK-8408 is C_{trough}.

8.4.1.3 Exploratory Endpoints

1. The emergence of RAVs to MK-3682 or MK-8408 when administered as part of a combination regimen.
2. The proportion of subjects with HCV RNA <LLOQ (either TD(u) or TND) at TW2, TW4, TW8, end of treatment, FW4, and FW8 after 12 weeks of treatment,.
3. The viral kinetics in the first 32 hours of treatment and Days 3 and 7 in the first 10 GT1-infected (two of whom are cirrhotics), 10 GT2, 10 GT3 (two of whom are cirrhotics) and up to five subjects each who are GT4, GT5 or GT6-infected who consent to participate. The collection of the viral kinetics in this subset of subjects will be used to explore the impact of early viral load decline on sustained viral response in each treatment arm as stated in the exploratory objective. The viral kinetics will be summarized, and the relationship of viral kinetics and likelihood of achieving SVR₁₂ response may be explored in the future after appropriately combining subjects with viral kinetic measurements from other studies.
4. The association between genetic variation (such as IL28 genetic variation) and the clinical response to the treatment(s) administered.
5. The proportion of HIV co-infected subjects who develop HIV-1 virologic failure during protocol therapy;
6. Change from baseline in CD4+ T-cell counts in the HIV co-infected population.

8.4.2 Safety Endpoints

An initial description of safety measures is provided in Section 4.2.3.2 and ECIs are defined in Section 7.2.3.2.

8.5 Analysis Populations

8.5.1 Efficacy Analysis Populations

Per Protocol (PP)

The PP population will serve as the primary population for the analysis of SVR₁₂ and SVR₂₄ in this study, since it provides a more accurate assessment of the virological efficacy in subjects who are reasonably compliant in this Phase 2 trial. The PP population excludes subjects due to important deviations from the protocol that may substantially affect the results of the primary and secondary efficacy endpoints. Non-virologic failures that are due to administrative reasons will be excluded. Potential violations that may result in the exclusion of a patient from the PP population include:

- The subject did not meet specific inclusion/exclusion criteria (for example, the subject is infected with a mixed GT infection or non-typeable genotype).
- The subject received concomitant medications that are prohibited due to their potential to result in a clinically significant lowering of the MK-3682 or MK-8408 concentrations (see Section 5.5 for specific details of prohibited medications). Further, any co-administered medication currently unidentified, but for which subsequent clinical DDI data indicate that co-administration with MKs leads to a clinically significant lowering of MK concentrations.
- Other violations may be identified during the course of data collection and they will be listed specifically in the CSR.

A subject with important deviations from the protocol at treatment allocation (Day 1) will be excluded from the PP population. For subjects with important deviations from the protocol as described above during the course of treatment, data obtained subsequent to the violation will be excluded from analysis.

Full Analysis Set (FAS)

The FAS population will serve as a supportive analysis of efficacy data in this study. The FAS population consists of all subjects who are assigned to a treatment arm and receive at least one dose of study treatment in this study.

Modified Full Analysis Set (mFAS)

The mFAS population will be used for the efficacy endpoints of SVR₁₂ and SVR₂₄ as a supportive analysis and for the endpoint of the proportion of subjects experiencing virologic failure at FW12 as a primary analysis. The mFAS population is a subset of the FAS population, with subjects excluded for study discontinuation for reasons unrelated to the treatment regimen. Examples include loss to follow-up, discontinuation from the study due to non-drug related AEs, informed consent withdrawal, and other non-virologic failures.

The final determination on the exclusion of subjects from various analysis populations will be made prior to the final database lock and will be documented in a separate memo.

Subjects will be included in the treatment arm to which they are allocated for the analysis of efficacy data using the FAS, mFAS, and PP populations. Details on the approach to handling missing data are provided in Section 8.6, Statistical Methods.

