3.2 Secondary Objective(s) & Hypothesis(es)

Objectives will be evaluated separately for each HCV GT.

- 1) **Objective:** To evaluate the efficacy of co-administered MK-3682 (450mg) + MK-8408 (60mg) following 12 weeks of treatment, as assessed by the proportion of subjects achieving SVR₂₄ (Sustained Virologic Response 24 weeks after the end of all study therapy), defined as HCV RNA < LLOQ 24 weeks after the end of all study therapy.
- 2) **Objective:** To evaluate the efficacy of 12 weeks of treatment with co-administered MK-3682 (450mg) + MK-8408 (60mg), as assessed by the proportion of subjects

who experience virologic failure (either on-treatment failure or relapse post-treatment) at Follow-up Week 12 among subjects who do not discontinue study for non-treatment-related (e.g., administrative) reasons.

- 3) **Objective:** To evaluate the effect of baseline resistance-associated variants (RAVs) in NS5A and/or NS5B on the efficacy of 12 weeks of treatment with co-administered MK-3682 (450mg) + MK-8408 (60mg), as assessed by the proportion of subjects with baseline RAVs achieving SVR₁₂.

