1. Treatment-Related Discontinuation = Failure (TRD=F) approach: Subjects with treatment-related missing data (type #2 above) will be considered as failure; whereas the subjects who have the non-treatment-related missing value (type #3 above) and who do not have virologic failure during the observed study period will be excluded from the analysis for the time points following their study withdrawal. Note that subjects with documented virologic failure during the treatment or follow-up period, even if they withdrew prematurely due to reasons not related to study drug, are classified as failures.
2. Missing=Failure (M=F) approach: Subjects with any non-intermittent missing data (i.e., type #2 and #3 above) will be imputed as failures, regardless of the reason for study discontinuation.

In addition, a missing baseline/Day 1 HCV RNA result will be replaced with a screening result, if available.

Proportions of Subjects With Virologic Responses and Virologic Failures

For the primary efficacy analysis, the proportions of subjects achieving SVR₁₂ after 12 weeks of treatment in each treatment arm will be provided and 95% confidence intervals for these rates will be calculated using the Clopper-Pearson method [49]. The same method will be used to analyze all binary endpoints including SVR₂₄ after 12 weeks of treatment.

For all analyses conducted using the PP and mFAS populations, the missing data approach of TRD=F will be utilized. In addition, for all analyses in these two populations, a subject will be considered to have achieved a particular endpoint if the HCV RNA levels for the infection he/she had at baseline are < LLOQ. In other words, if a subject has HCV RNA levels \geq LLOQ at a particular time point, but those RNA levels correspond to an infection that is of a different genotype and/or subtype compared to the infection detected at baseline and the baseline infection has been cleared, then the subject is considered to have achieved response for the given endpoint.

Sensitivity analyses that use the FAS population will utilize the M=F missing data approach. Also, in the FAS analyses, only subjects with HCV RNA levels < LLOQ for any type of HCV infection at a given time point will be considered to have achieved the endpoint.

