PP (Primary for SVR ₁₂ and SVR ₂₄)	HCV RNA < LLOQ for baseline infection HCV RNA ≥ LLOQ demonstrated to be due to reinfection (after clearance of baseline infection)	HCV RNA ≥ LLOQ for baseline infection*	Subject with important deviations from the protocol including subject discontinued from the study for non-treatment related reasons and other violations such as violation of I/E criteria, use of prohibited concomitant medications (see Section 8.5.1)
mFAS (Supportive for SVR ₁₂ , SVR ₂₄ ; Primary for proportion of subjects experiencing virologic failure at FW12)	HCV RNA < LLOQ for baseline infection HCV RNA ≥ LLOQ demonstrated to be due to reinfection (after clearance of baseline infection)	HCV RNA ≥ LLOQ for baseline infection*	Subject discontinued from the study for non-treatment related reasons.
FAS (Supportive for SVR ₁₂ and SVR ₂₄)	HCV RNA < LLOQ	HCV RNA ≥ LLOQ	Subject did not receive at least one dose of study medication
mFAS = modified Full Analysis Set FAS = Full Analysis Set PP = Per Protocol LLOQ = Lower limit of quantification *Baseline infection: Genotype(s) and subtype(s) present at baseline based on population sequencing and genotyping assay			

Subject Virologic Failure: Non-response, Rebound, Virologic Breakthrough, Relapse and Reinfection

Summary statistics will be provided to describe the rates of occurrence of subject non-response, rebound, virologic breakthrough, and relapse. Definitions for subject non-response, rebound, virologic breakthrough, and relapse are in Section 4.2.3.1.1.2. Reinfection will be defined as having detectable virus of a different genotype than that detected at baseline as determined by sequencing. Those with reinfection will be considered treatment success in the mFAS and PP analyses as long as the baseline infection was achieved HCV RNA < LLOQ.

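### The mFAS definition, Table 16 and the FW12 failure-rate denominator exclude unrelated leavers with no time limit and no exception for documented virologic failure, which conflicts with the TRD=F rule used in the same analyses

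*Combined protocol and SAP*

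**What the plan says.** Two sets of rules decide who counts in the PP and mFAS analyses.

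**Population and endpoint definitions.**
- Section 8.5.1 forms the mFAS from the FAS "with subjects excluded for study discontinuation for reasons unrelated to the treatment regimen". Its examples end with "informed consent withdrawal, and other non-virologic failures".
- Table 16 (8.6.1) gives the exclusion criterion for both mFAS and PP as a "subject discontinued from the study for non-treatment related reasons"; the PP cell adds other protocol deviations.
- The secondary failure-rate objective (3.2) is restricted to subjects "who do not discontinue study for non-treatment-related (e.g., administrative) reasons". Sections 4.2.3.1.1.1 and 8.4.1.1 carry the same restriction.

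**Missing-data rule.** TRD=F (8.6.1) applies to all PP and mFAS analyses.
- Unrelated leavers without virologic failure "will be excluded from the analysis for the time points following their study withdrawal".
- Subjects with documented failure on treatment or in follow-up, "even if they withdrew prematurely due to reasons not related to study drug, are classified as failures".

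The PP text in 8.5.1 sits closer to the second set. It says "Non-virologic failures that are due to administrative reasons will be excluded", and for deviations that arise during treatment it drops only later data: "data obtained subsequent to the violation will be excluded from analysis".

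PP is the primary population for SVR12 and SVR24. mFAS is the primary population for the FW12 failure rate, and the only one listed for it in Table 15.

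**The concern.** The first set of rules acts on the subject, once. The second acts on the subject at a given time point, and depends on whether failure has been documented. If the population flag is built first from Table 16, the TRD=F provisions for unrelated leavers have nobody left to act on.

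Two kinds of subject are then classified differently:
- a subject with confirmed relapse at FW4 who later withdraws for a reason coded as unrelated;
- a subject with observed SVR12 who is lost between FW12 and FW24.

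Two programmers working from different paragraphs could therefore report different primary results. For the relapser, the difference always favours the regimen. In an estimation study with no formal hypotheses, the point estimates and intervals are the result. The trial is open-label, the sponsor may look at efficacy as it accrues (8.2), and exclusions are settled in a memo before lock (8.5.1). The rule should not still be open to choice at that stage.

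**Working it through.** **Step 1. Three subjects under each rule.**

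| Subject | Mentioned in mFAS text, Table 16 or denominator as | TRD=F (8.6.1) |
|---|---|---|
| A: relapse confirmed at FW4, then unrelated withdrawal | Excluded if read literally | Failure for SVR12, SVR24 and the FW12 failure rate |
| B: SVR12 observed, lost before FW24 | Excluded from every time point if read literally | Responder for SVR12; excluded for SVR24 only |
| C: no failure, lost before FW12 | Excluded | Excluded |

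The rules agree only on C. For A, the PP text in 8.5.1 sides with TRD=F, because A is a virologic failure and that text removes only non-virologic failures. The PP cell of Table 16 does not carry this limit, so PP is described in two ways.

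**Step 2. Reproduce the plan's figures.** Section 8.9.1 assumes 10% protocol violations. This gives 50 × 0.90 = 45 PP subjects in Arms 1 to 4, and 25 × 0.90 = 22.5 in Arms 5 and 6, stated as 22. The Clopper-Pearson limits for x out of n are the 2.5% quantile of Beta(x, n − x + 1) and the 97.5% quantile of Beta(x + 1, n − x). All eight rows of Table 19 reproduce, including 43/45 = 95.6% (84.9 to 99.5) and 20/22 = 90.9% (70.8 to 98.9).

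**Step 3. Drop k relapsers.** SVR12 becomes x/(n − k) and the failure rate (n − x − k)/(n − k). The value of k is an assumption. The documents do not give the mFAS size, so the PP sizes stand in for it in the failure-rate column.

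| Start | k | SVR12 (95% CI) | Failure rate (95% CI) |
|---|---|---|---|
| 43/45 | 0 | 43/45 = 95.6% (84.9 to 99.5) | 2/45 = 4.4% (0.5 to 15.1) |
| | 1 | 43/44 = 97.7% (88.0 to 99.9) | 1/44 = 2.3% (0.1 to 12.0) |
| | 2 | 43/43 = 100% (91.8 to 100) | 0/43 = 0% (0 to 8.2) |
| 20/22 | 0 | 20/22 = 90.9% (70.8 to 98.9) | 2/22 = 9.1% (1.1 to 29.2) |
| | 1 | 20/21 = 95.2% (76.2 to 99.9) | 1/21 = 4.8% (0.1 to 23.8) |
| | 2 | 20/20 = 100% (83.2 to 100) | 0/20 = 0% (0 to 16.8) |

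**Step 4. Drop late-lost responders.** SVR12 becomes (x − k)/(n − k). From 43/45, losing one, two or three gives 42/44 = 95.5%, 41/43 = 95.3% or 40/42 = 95.2%. From 20/22, it gives 19/21 = 90.5%, 18/20 = 90.0% or 17/19 = 89.5%. The change is at most 0.3 points in the larger arms and 1.4 in the smaller, and it goes against the regimen.

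**The case against.** The strongest reply is that the plan already answers the question. TRD=F addresses the relapser who withdraws, in terms, and applies to every PP and mFAS analysis. A specific rule should outweigh cells in a table that the SAP itself calls a summary, and a reading that leaves two deliberate sentences without effect should be rejected. The PP text and the mFAS examples both speak of non-virologic failures. Section 8.5.1 sends the reader to 8.6 for missing data. A relapser who leaves because treatment failed may also count as a treatment-related discontinuation, since that category covers efficacy reasons, and would then be a failure under either rule. FAS with M=F keeps every dosed subject, and relapse rates are summarised separately.

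Most of this stands. It shows that TRD=F is very probably the intent, and that a relapser is at risk only if the reason for leaving is coded as unrelated. Three points remain:
- The pointer to 8.6 does not state precedence, and Table 16 is a natural source for the population flags.
- FAS with M=F is a partial safeguard for SVR12. It also counts ordinary unrelated leavers as failures, so a gap between PP and FAS would not identify dropped relapsers. Table 15 lists no FAS analysis of the failure rate, and the descriptive relapse summaries name no population.
- The failure-rate denominator contains the unqualified exclusion in the endpoint definition itself.

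A reader might infer that the plan removes every unrelated leaver, relapsers included, or that relapsers will tend to withdraw because no rescue treatment is specified. The documents support neither. The first ignores the PP text and TRD=F. For the second no rate is given, and 7.1.5.4 has relapsers return for their remaining follow-up visits.

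**Conclusion.** This is an internal inconsistency to correct before database lock. The loss of relapsers is one literal reading of conflicting text and not the declared plan.

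The FW12 failure rate is the most exposed result, because its own denominator carries the exclusion and mFAS is its only listed analysis. SVR12 is less exposed, given the PP text and the FAS analysis.

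The effect is zero if no relapser withdraws for a reason coded as unrelated. Each one dropped from an arm of 45 with two failures raises SVR12 by about 2.2 points (97.7 or 100 against 95.6). In an arm of 22 with two failures, the first adds 4.3 points and both together 9.1. The two-of-two case is a worst case chosen for illustration, not a forecast. The late-lost responder shows the time-point conflict clearly but hardly moves the estimate. No error rate, power or sample size is affected.

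**What to change.** In the mFAS definition (8.5.1), both exclusion cells of Table 16, and the failure-rate endpoint (3.2, 4.2.3.1.1.1 and 8.4.1.1), limit this exclusion to subjects who meet both conditions:
- they left the study for a non-treatment-related reason before the time point of the endpoint;
- they had no documented virologic failure at or before that time point.

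Define separate population flags for SVR12, SVR24 and FW12 failure. Add one sentence saying that the TRD=F rule in 8.6.1 prevails if a population definition appears to differ. The separate PP exclusions for other protocol deviations need not change.

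The cost is a few lines of text and endpoint-specific flags in the programming. No data collection, visit or sample size changes. Compared with the literal reading, reported SVR12 may be lower in any arm where a relapser has withdrawn.

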3.0 OBJECTIVE(S) & HYPOTHESIS(ES)

3.1 Primary Objective(s) & Hypothesis(es)

This is an estimation study; there are no formal hypotheses.

In subjects infected with each HCV genotype:

- 1) **Objective:** To evaluate the efficacy of co-administered MK-3682 (450mg) + MK-8408 (60mg) following 12 weeks of treatment as assessed by the proportion of subjects achieving SVR₁₂ (Sustained Virologic Response 12 weeks after the end of all study therapy), defined as HCV RNA < LLOQ 12 weeks after the end of all study therapy.
- 2) **Objective:** To evaluate the safety and tolerability of co-administered MK-3682 (450mg) + MK-8408 (60mg).

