5.3 Randomization or Treatment Allocation

All subjects will receive a treatment regimen of MK-3682 (450mg) + MK-8408 (60mg) co-administered concomitantly as separate medications once-daily for 12 weeks. Subjects will be assigned to treatment arms based on genotype.

Documentation of treatment period entry will occur centrally using a computer generated allocation schedule to assign a treatment/allocation number.

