7.1.3.3 HCV Evaluation

The following specimens are to be obtained as part of Efficacy/Pharmacogenetic Measurements:

- Samples for HCV Genotype evaluation must be obtained for inclusion in the study. All baseline samples will be genotyped using the FDA approved Abbott HCV Real Time Genotype II assay which detects HCV genotypes 1a, 1b, 2, 3, 4, 5, and 6 through the use of genotype-specific fluorescent-labeled oligonucleotide probes in a real-time RT-PCR assay. The RT-PCR reaction uses 3 sets of HCV specific amplification primers targeting the conserved 5'UTR (for all genotypes) and NS5B regions from GT1a and 1b. The assay has accuracy of >96% for GT1, 1a, 1b, 2, 3 and 4, 89% for GT5 and 83% for GT6 with 100% specificity in HCV serologically negative plasma samples. Phylogenetic analyses will be performed using sequences for NS3, NS5A and NS5B to ensure accurate assignment of sample genotype/subtype.
- Blood must be drawn from each subject to assess HCV RNA plasma levels at various time points as shown in the study flow chart. HCV RNA in plasma will be measured using a COBAS™ AmpliPrep/COBAS™ Taqman™ HCV Test, v2.0 ® assay with a lower limit of quantification (LLOQ) of 15 IU/mL. Leftover plasma may be used for viral resistance testing if needed. Also, leftover plasma may be used for future biomedical research only if the subject signed for future biomedical consent.
- Blood must be drawn from each subject to assess viral resistance mutation and processed as instructed by the central laboratory manual. Leftover plasma may be used for future biomedical research only if the subject signed for future biomedical consent.

- Protein and metabolites may be measured from blood samples to compare biomarkers measured prior to treatment, to biomarkers measured at several time points during treatment that correlate with subject response to treatment (e.g., sustained viral response).
- Samples collected for genetic analysis are obtained at Day 1. Any leftover DNA may be used for future biomedical research only if the subject signed for future biomedical research consent.

Note: Samples may also be used for future assay development and validation if the subject signed for future biomedical research consent.

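### Efficacy is analysed by allocated genotype arm, and no rule says where a subject belongs when the planned sequence result disagrees with that arm

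*Combined protocol and SAP*

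**What the plan says.** The primary objective (Section 3.1) is set "In subjects infected with each HCV genotype". Section 5.3 gives everyone the same regimen and adds: "Subjects will be assigned to treatment arms based on genotype". Section 5.4 confirms that there is no randomisation.

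On genotyping, Section 7.1.3.3 says "Samples for HCV Genotype evaluation must be obtained for inclusion in the study". It rates the assay above 96% accurate for GT1 to GT4, and "89% for GT5 and 83% for GT6 with 100% specificity in HCV serologically negative plasma samples". The same bullet continues: "Phylogenetic analyses will be performed using sequences for NS3, NS5A and NS5B to ensure accurate assignment of sample genotype/subtype". It does not say when the sequence result is available or what follows if it disagrees with the assay.

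Section 8.5.1 then fixes the analysis group: "Subjects will be included in the treatment arm to which they are allocated for the analysis of efficacy data". This covers FAS, mFAS and PP. Its genotype example of a PP exclusion is mixed or non-typeable infection.

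Sequencing enters the analysis only when response is judged. Section 8.6.1 counts quantifiable RNA as a response if the baseline infection has cleared and "those RNA levels correspond to an infection that is of a different genotype and/or subtype compared to the infection detected at baseline". Later in the same section: "Reinfection will be defined as having detectable virus of a different genotype than that detected at baseline as determined by sequencing". The footnote to Table 16 defines baseline infection by genotype and subtype, from sequencing and assay together.

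**The concern.** An as-allocated analysis normally protects a randomised comparison. Here there is none: genotype is a baseline trait, and the arm is a label for it. Keeping subjects where they were allocated therefore keeps whatever genotype call was made at entry, right or wrong, although the plan intends to obtain a better one.

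PP does not clearly catch the problem. Inclusion criterion 3 accepts any single genotype from 1 to 6. A subject placed in Arm 6 who sequences as one other genotype breaks no entry criterion and does not match the PP example.

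At stake are the per-genotype SVR12 estimates, chiefly in Arms 5 and 6, which have the fewest subjects and the lowest stated assay accuracy. The GT1a/GT1b subgroup in Section 8.10 needs the same definition, since a subtype error leaves the arm unchanged but moves the subject between subgroups.

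**Working it through.** **The plan's own figures.** Section 8.9.1 assumes 10% protocol violations: 50 × 0.9 = 45, and 25 × 0.9 = 22.5, stated as about 22. The Clopper-Pearson limits are the 2.5% quantile of Beta(x, n − x + 1) and the 97.5% quantile of Beta(x + 1, n − x). All eight Table 19 intervals reproduce to one decimal, for example 20/22 = 90.9% (70.8 to 98.9). The arithmetic is sound; the gap is in classification.

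**Weight of one subject.** 1/22 = 4.5 points in Arms 5 and 6; 1/45 = 2.2 points in Arms 1 to 4.

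**Which call sets the arm.** In the Section 6.0 flow chart, genotype determination is at screening only, allocation is on Day 1, and plasma for viral resistance is first drawn on Day 1. This points to allocation on the assay result, with sequencing afterwards. It is an inference.

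**How many could be misplaced.** The documents do not give the wrong-genotype share of any arm. Two readings of accuracy show how far the answer depends on assumption.

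- Assume the whole shortfall is wrong-genotype subjects inside the arm. Arm 6: 25 × (1 − 0.83) = 4.25. Arm 5: 25 × (1 − 0.89) = 2.75. Arms 1 to 4: fewer than 50 × (1 − 0.96) = 2 each.
- Assume instead that accuracy is the share of true samples typed correctly. The shortfall for GT6 is then GT6 subjects who go elsewhere or get no result, and errors inside Arm 6 come from other genotypes. With screening in proportion to the targets (200 GT1 to GT4, 25 GT5, 25 GT6), 96% accuracy for GT1 to GT4, and half of all GT1 to GT5 errors called GT6, wrong entries are 0.5 × (200 × 0.04 + 25 × 0.11) = 5.375 and correct entries are 25 × 0.83 = 20.75. The wrong share is 5.375/26.125 = 21%. If no errors are called GT6, it is 0. The assumed split drives the result.

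**Effect on the estimate.** Expected bias = wrong share × (SVR12 of the other genotype − SVR12 of the named genotype). With a 17% share in Arm 6:

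- named 95%, other 70%: 0.17 × (−25) = −4.25 points
- named 70%, other 97%: 0.17 × 27 = +4.6 points
- equal rates: 0

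With 11% in Arm 5, the same pairs give −2.75 and +3.0 points. The response rates are assumptions.

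**Effect on one result.** Suppose Arm 6 shows 20/22, 4 subjects sequence as another genotype, and none move in:

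- both failures truly GT6: 16/18 = 88.9% (65.3 to 98.6)
- one truly GT6: 17/18 = 94.4% (72.7 to 99.9)
- neither: 18/18 = 100% (81.5 to 100)

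**Reinfection wording.** Take GT1a cleared, then GT1b detected. The response rule in Section 8.6.1 covers a change of subtype, so this is a response. Table 16 judges response on the baseline infection, defined by genotype and subtype, and agrees. Only the sentence defining reinfection, which names genotype alone, withholds the label.

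**The case against.** Several objections have force.

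The source of allocation is not stated. Section 7.1.3.3 lets leftover HCV RNA plasma, first drawn at screening, be used for resistance testing, so sequencing before allocation is not ruled out. If sequence always set the arm, the problem would vanish. This stands as a limit on certainty, but the plan would still need to say so.

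PP exclusions are open-ended. Section 8.5.1 lists potential violations, allows others to be found later, and has exclusions settled in a memo before database lock; Section 8.0 allows a supplemental SAP. A discordant subject could be handled by these routes. None names the case, and excluding a subject does not return that subject to the correct genotype group.

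A reader might infer from the accuracy figures that about 4 of 25 Arm 6 subjects will be the wrong genotype. The documents do not support that: 83% may be the share of true GT6 samples typed correctly, or may include samples with no result.

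A reader might also picture both failures in a 20/22 result being misassigned, so that the estimate becomes 100%. That is an extreme case. Even with 4 of 22 misassigned, if failure is unrelated to misassignment the chance is C(4,2)/C(22,2) = 6/231 = 2.6%.

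As-allocated grouping also has a use: arm membership drives the enrolment-stopping and 16-week extension rules in Sections 5.11.3 and 5.12.1. That supports retaining an as-allocated analysis, but not making it the only one.

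**Conclusion.** The gap is real and modest. The plan estimates response by genotype, intends to obtain a more reliable genotype, and has no rule for using it to place subjects. Errors can run in either direction, into or out of an arm. The 4-of-25 and 3-of-25 figures are what one assumption gives; they are neither forecasts nor limits. The bias calculation rests on assumed response differences, and whether genotypes differ is what the trial is meant to show.

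A reader might take the reinfection wording as a conflict that flips primary outcomes. It is narrower: the operative response rule and Table 16 agree, and one defining sentence needs alignment.

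This is an estimation study with no formal hypothesis and no success threshold. The change is worth making because it is cheap; the trial's validity does not hang on it.

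**What to change.** In Section 8.5.1, define the analysis genotype and subtype for PP and mFAS efficacy, including the GT1a/GT1b split, as the sequence-confirmed baseline result, using the assay result where sequencing fails. Keep FAS by allocated arm as a sensitivity analysis. List discordant subjects with allocated arm, sequenced genotype and the treatment duration received. In the Section 8.6.1 definition of reinfection, replace genotype alone with genotype and/or subtype, to match the response rule and the Table 16 footnote.

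The cost is SAP wording and one listing, since the sequencing is already planned. Group sizes may shift by a few subjects from those in Table 19. If one arm is extended to 16 weeks, a reclassified subject may have had a different duration from the rest of that genotype group, which is why the listing should show duration.
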